---

## APPENDICES

---

## 1. Summary

In 2008, over half of all pregnancies in the United States were unintended, representing an increasing incidence over the prior decade. Research has shown that when contraception is provided at no cost, women are more likely to use medical contraception and to choose more effective and more expensive methods over less effective, less expensive methods. The Patient Protection and Affordable Care Act (PPACA) mandates that most women of reproductive age with private health insurance have full contraceptive coverage with no out-of-pocket costs, creating an actionable time for women to evaluate their contraceptive choices without cost considerations.

The MyNewOptions study is a three-arm randomized controlled trial designed to test web-based interventions aimed at assisting privately insured women make contraceptive choices consistent with their reproductive goals. Privately-insured women between the ages of 18 and 40 not intending pregnancy will be randomly assigned to one of three groups: 1) a reproductive life planning (RLP) intervention, 2) a reproductive life planning enriched with contraceptive action planning (RLP+) intervention, or 3) an information only control group. Both the RLP and RLP+ will guide women to identify their individualized reproductive goals and contraceptive method requirements. The RLP+ additionally includes a contraceptive action planning component, which uses if-then scenarios that allow the user to problem solve situations that make it difficult to be adherent to their contraceptive method. All three groups will have access to a reproductive options library, containing information about their contraceptive coverage and the attributes of alternative contraceptive methods. Women will complete a baseline survey and follow-up surveys every 6 months over 2 years concurrent with intervention boosters. Study outcomes include contraceptive use and adherence.

Results from the MyNewOptions study will demonstrate whether web-based reproductive life planning, with or without contraceptive action planning, helps insured women make patient-centered contraceptive choices compared with an information-only control condition.

## **2. Background and Rationale**

### **2.1. General Overview: Unintended Pregnancy in the U.S.**

Avoiding unintended pregnancy is important to women due to the adverse associated personal, economic, and health consequences. In 2006, 49% of U.S. pregnancies were unintended, which has not improved since 1994 and is the highest among developed countries. In 2001, 42% of unintended pregnancies resulted in abortion. Women with unintended pregnancies are more likely to have delayed or no prenatal care, smoke or drink alcohol during pregnancy, experience depression or domestic violence during pregnancy, and are less likely to breastfeed. Births associated with unintended pregnancies are associated with increased likelihood of preterm birth, low birth weight, and other negative physical and mental health outcomes for women and children. The U.S. Department of Healthy People 2020 campaign has set the goal of reducing the proportion of pregnancies that are unintended from 49% of pregnancies to 44% of pregnancies by 2020, however no clear strategy for achieving this goal currently exists.

### **2.2. Why Unintended Pregnancies Occur: Contraceptive Use, Discontinuation, and Adherence**

Unintended pregnancies occur when contraception is not used, not used continuously, not used perfectly (adherence), or when contraceptive failure occurs. Contraceptive nonuse is often due to access barriers, such as not having a regular health care provider or insurance coverage. The Patient Protection and Affordable Care Act (ACA) removes the cost barrier for most privately insured women, as it requires all FDA-approved contraceptive methods (including sterilization) and contraceptive counseling to be provided without copays or deductibles. Prior studies have shown that when contraception is provided at no cost to the patient, more women tend to choose the more effective and more expensive methods over less effective, less expensive methods.

Discontinuation and poor adherence occur commonly—a decision analysis estimated that 20% of the 3.5 million unintended pregnancies that occur each year in the U.S. are attributable to poor adherence or discontinuation of oral contraceptives. Discontinuation occurs when side effects and health concerns arise that could be addressed with more individualized contraceptive counseling aimed at reassuring women about the nature of side effects and how to manage them, or assisting women with the selection of another method. Poor adherence occurs when women use contraceptives that do not suit their lifestyle (e.g., requiring frequent ongoing action) or they have poor self-regulation skills needed to achieve better adherence. Based on these reasons for contraceptive failures, our intervention includes goal-setting (through reproductive life planning) and skills building (through action planning) to help women improve contraceptive adherence for their chosen contraceptive method.

### **2.3. Previous Interventions for Improving Contraceptive Continuation and Adherence**

Systematic reviews of interventions aimed at improving continuation or adherence to hormonal methods of contraception have found that few interventions are effective. However, these older interventions were aimed at improving continuation and adherence to methods that women were already using (without determining if they were the methods

best suited for each individual woman), were not theoretically-based, did not include skills building, and did not remove out-of-pocket contraceptive cost.

The Contraceptive CHOICE Project is an ongoing research study based on the premise that women would choose more effective contraceptive methods if provided at no cost. This St. Louis-based intervention project has enrolled nearly 10,000 women who: (1) received structured contraceptive counseling aimed at promoting the most effective methods—long-acting reversible contraceptives (LARCs) and (2) were provided free access to all contraceptive methods. In the CHOICE Project, 75% of participants chose a LARC (compared with 5% nationally), with early results demonstrating a significant decline in unintended pregnancy with an abortion rate among participants that is one-fifth of the national level. While structured contraceptive counseling aimed at promoting LARCs in the context of free access to contraceptive methods is effective at reducing unintended pregnancy, structured face-to-face counseling is not easily disseminable. In the CHOICE Project, contraceptive counselors underwent 6 hours of training, and on average the structured contraceptive counseling took 13 minutes per participant. Even with ACA-mandated coverage for contraceptive counseling, it is not feasible to add 13 minutes of face-to-face counseling for contraception in most current primary care practices. Other less labor-intensive models need to be developed and tested for real world effectiveness that can be easily disseminated and minimize use of provider time, given the already limited resources in clinical settings. Also, the CHOICE Project promoted the use of LARCs—our approach is to encourage women to use the contraceptive method that best suits their individual reproductive goals and personal contraceptive requirements.

#### **2.4. Innovation and Potential for Improvement through Research**

This study is innovative for a number of reasons. First, we partner with a major private health insurer—*Highmark Health*—to test an intervention aimed at helping women formulate and achieve their reproductive goals. The ACA mandates that private health insurers provide full coverage for all FDA-approved contraceptive methods and counseling, making insurers major stakeholders in ensuring access to contraceptive services. By partnering with Highmark, we are also able to measure contraceptive adherence with medication possession ratios (MPRs) using pharmacy claims data. Second, we will conduct the first systematic assessment of “reproductive life planning,” a practice endorsed by the Centers for Disease Control and Prevention (CDC) and reproductive health experts to help women achieve their personal reproductive goals. The CDC has called for the development and evaluation of reproductive life plan tools, but none have been formally tested. Third, we will integrate “action planning” (also known as “if-then planning,” “implementation intentions,” or “contingency planning”), into a reproductive life planning intervention for improving contraceptive adherence. Fourth, the intervention will be *entirely online*, making it easy to disseminate while avoiding barriers to providing behavioral change interventions in health care settings, including a lack of time and counseling skills on the part of primary care providers.

#### **2.5. Impact on Health Care Performance**

Our traditional methods for providing contraceptive counseling have been in clinical settings with face-to-face interactions between patients and health care providers—usually primary care providers, gynecologists, family planning providers/counselors, or nurses. However, primary care providers, who are the point of first contact for privately insured

women, often lack comprehensive knowledge of the full range of contraceptive options and may not be well informed about method effectiveness. For example, primary care providers underestimate the rate of unintended pregnancy and the risk of pregnancy associated with commonly used contraceptive methods, and even gynecologists may have incorrect knowledge about the risks associated with IUD use. Thus, in addition to the challenge of lack of time in primary care visits, face-to-face contraceptive counseling in primary care settings may not be optimal or patient-centered.

With the rise in Americans using the Internet as a source of medical information, web-based tools could be effective in addressing a variety of health issues. According to the Pew Internet and American Life Project, 81% of U.S. adults had access to the Internet in 2012. Women are more likely than men to use the Internet for health information, with the highest percentage among women aged 25-34 (65.8%). Web-based approaches may be desirable for women because they are private and avoid disclosing personal or sexual information to a provider. A computerized tool for reproductive life planning could potentially be more patient-centered than a tool disclosed to a health care provider, in that it makes no judgments about a woman's plans. While not all insured women in our target age group will have access to the Internet or even desire using the Internet to receive health information, this is a modality that has potential to reach a large and growing segment of the target population and should be explored.

## 2.6. Listening Sessions

Women in our target population aided in the development of the RLP and RLP+ interventions. Listening Sessions (focus groups) were conducted with reproductive-age women who were privately insured, sexually active, not currently pregnant or trying to get pregnant in the next year, and had not had a hysterectomy or tubal ligation. Participants included women who had not had children and women who reported having completed childbearing. Most of the women were using oral contraceptives. First, we sought input for adapting the CDC's reproductive life plan tool into a patient-centered, interactive web-based format designed to help women formulate their reproductive goals and identify their personal requirements for contraception. Second, we sought feedback on the content of an action planning exercise aimed at improving contraceptive continuation and adherence through skill-building. The ideas generated from the listening sessions shaped the development of the RLP and RLP+ interventions.

Our listening session participants were enthusiastic that the RLP was a useful tool. Women reported it was helpful to put their reproductive goals down on paper—one participant said, *“When I started having kids I didn't think about myself at all. This made me think about myself, it made me think of my needs as a mom and a person—that is really helpful.”* The listening session participants were overwhelmingly positive that the RLP tool could help them with contraceptive decision-making, because it was difficult for them to find time to seek contraceptive counseling with their health care providers—*“my biggest issue is finding time to have a provider. It is too hard for women who are working or have kids.”* Several of the women reported that they used birth control pills because they had comfortably used them for a long time, and were not as familiar with the newer methods—*“there are always new forms of birth control. It would be helpful to learn about what the website would suggest for me.”* Other women were aware that there were myths about IUDs that have been disproven (*“they don't make women infertile anymore”*), but they did not have enough information to know if IUDs were a good choice for them. Additionally, they

were reluctant to consider certain methods because of the cost, and were largely unaware that their insurer now covers the cost of contraception without copays. Several of the women were surprised to learn that the typical failure rate in the first year of oral contraceptives use was as high as it is—*“I like the visual [for communicating pregnancy risk], but it makes birth control pills look less effective than I want them to be.”* Another woman said, *“Everyone assumes their method is better than it really is.”* At the end of the listening sessions, women either validated their current contraceptive method choice (*“I’m a perfect [pill] user, I use it well, I don’t forget to take it, so it works for me.”*) or were considering that other methods may be better suited for their needs (*“This helped me think the IUD is better for me.”*).

### 3. Overview of Trial Design

#### 3.1 Design

MyNewOptions is a two-year, three-arm parallel group design randomized controlled trial testing a Reproductive Life Planning web-based intervention (RLP) vs. a Reproductive Life Planning plus action planning intervention (RLP+) vs. an information only control group.

The inclusion criteria are (1) women; (2) privately insured through Highmark Health; (3) age 18 – 40; (4) Pennsylvania residents; (5) not covered by an employer group with a religious exemption; (6) Internet access; (7) sexually active (within the past 6 months or expected in the next 6 months); and (8) wish to avoid pregnancy for at least the next 12 months. Women were excluded if they had a tubal ligation, hysterectomy, a partner with a vasectomy or if they are unable to read and write English.

##### 3.1.1. Primary Hypothesis and Primary Outcome

Compared with random assignment to an information only control group, random assignment to a reproductive life planning tool (RLP) or a reproductive life planning tool plus a contraceptive action planning tool (RLP+) will increase contraceptive use and adherence. The primary outcome variable is contraceptive use when not intending pregnancy, defined as whether the participant is using any contraceptive method to prevent pregnancy (e.g., hormonal methods, barrier methods, withdrawal, natural family planning, etc.).

##### 3.1.2. Secondary Hypotheses

Compared with random assignment to an information only control group, random assignment to a reproductive life planning tool (RLP) or a reproductive life planning tool plus a contraceptive action planning tool (RLP+) will:

- Lead to the use of more effective contraception
- Result in more continuous use and better method adherence during the two year study period.
- Improve contraceptive method satisfaction
- Result in lower rates of unintended pregnancy (exploratory outcome)

##### 3.1.3. Interventions

Privately-insured women between the ages of 18 and 40 not intending pregnancy will be randomly assigned to one of three groups: 1) a reproductive life planning (RLP) intervention, 2) a reproductive life planning enriched with contraceptive action planning (RLP+) intervention, or 3) an information only control group. Both the RLP and RLP+ will guide women to identify their individualized reproductive goals and contraceptive method requirements. The RLP+ additionally includes a contraceptive action planning component, which will utilize if-then scenarios to help users problem solve situations that make it difficult to be adherent to their preferred contraceptive method. All three groups will have access to a reproductive options library, containing information about their contraceptive coverage and available contraceptive methods. Women will participate in the study for two years, completing a baseline survey and follow-up surveys every 6 months concurrent with intervention boosters.

### **3.1.4. Patient Engagement**

Patient engagement is a critical component of this trial. We will convene a group of 10-12 women who will meet the same eligibility criteria as our research participants. These women will meet with investigators six times over the course of the research study to help develop each aspect of the research study.

### **3.1.5. Provider Engagement**

We will convene a group of 10-15 health care providers (women and men) who will advise us on critical aspects of this research study. These women and men will meet with investigators three times over the course of the research study to discuss study results, dissemination of findings, and future directions for the research study.

### **3.1.6. Study Population**

The MyNewOptions study will recruit women with private health insurance between the ages of 18 and 40. The specific inclusion and exclusion criteria are described in section four. These criteria are intended to select a population that is at risk of experiencing an unplanned pregnancy.

## **3.2. Sample Size Justification**

The planned sample size for the study is 972 randomized participants (324 for each of the three study groups). The binomial regression analysis described for the binary outcomes of Specific Aim 1 drive this sample size calculation because binary outcomes contain the least amount of information (and hence, yield the lowest statistical power). The assumptions that lead to this sample size of 972 randomized participants are as follows:

1. binomial regression with the proportion of occurrences out of four time points
2. 90% statistical power
3. two-sided, 0.025 significance level test (Bonferroni correction) comparing RLP to control, RLP+ to control, and RLP to RLP+ within each stratum
4. effect size of 0.10 (difference between rates of 0.25 and 0.35)
5. 10% lost to follow-up per year, 10% lost per year for women who change their minds about intending pregnancy, and another 10% lost per year for those women who become pregnant (intentionally or unintentionally)

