#### **6.3.2. Randomization Scheme**

Each eligible participant will be randomized to one of the three study conditions by means of a permuted-block algorithm to achieve 1:1:1 allocation into one of the following groups: 1) RLP, 2) RLP+, or 3) information only (control).

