### 11.3. Analytic Methods

#### 11.3.1. Specific Aim 1

The outcome variables are binary (contraception use; satisfied with contraceptive method) and ordinal (contraceptive method effectiveness), and will be measured at four time periods post-baseline (6, 12, 18, and 24 months). For the binary outcome variables, we will construct a proportion for each participant as the number of time periods in which the participant's response is positive, divided by the number of time periods in which the participant is not intending pregnancy. The denominator will be four, except for those participants who withdraw consent from the study, change their minds about intending pregnancy during the study, or become pregnant. Therefore, we will apply a binomial regression analysis to these proportions. We will use intervention group assignment (intention-to-treat analysis) as the sole regressor in the primary analysis, but we will investigate in secondary analyses the effects of selected covariates on the proportional response (demographics; pregnancy history; sexual and contraceptive history; perceived control/fatalism toward contraception; relationships; compliance with log-in requirements). In terms of the three randomized groups, we will construct two-sided test statistics for comparing: 1) RLP to control, 2) RLP+ to control, and 3) RLP to RLP+. Therefore, we will impose a Bonferroni correction factor to the significance level ( $\alpha = 0.0167$ ). We will apply additional secondary analyses that are longitudinal, in which we invoke a logistic regression model with random participant effects to investigate if there are any time period effects and/or time period by intervention interactions for the binary outcomes. Finally, we will invoke a shared parameter model to account for the informative censoring that could occur due to participant withdrawal in a longitudinal study. In our setting, the shared parameter model includes a Weibull time-to-event regression model for the time to participant withdrawal in conjunction with a logistic regression model with random participant effects for the binary outcome.

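### The sample size rests on a 0.025 test level, but the same three comparisons will be tested at 0.0167, so 972 women give about 87% power, not the stated 90%

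*Protocol*

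**What the plan says.** Protocol section 3.2 plans 972 randomised women, 324 in each of three arms, and says that the binomial regression for the binary Aim 1 outcomes drives this number. Its assumptions include "90% statistical power", rates of 0.25 and 0.35, four time points, and a "two-sided, 0.025 significance level test (Bonferroni correction) comparing RLP to control, RLP+ to control, and RLP to RLP+ within each stratum". It also allows three separate losses of 10% per year: loss to follow-up, changed pregnancy intention, and pregnancy.

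Protocol section 11.3.1 describes the analysis of those outcomes. It lists the same three two-sided pairwise comparisons and then says "we will impose a Bonferroni correction factor to the significance level", giving the level as 0.0167. Randomised group is the only regressor in the primary analysis.

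Protocol section 6.3.2 allocates women "by means of a permuted-block algorithm to achieve 1:1:1 allocation into one of the following groups" and names no stratification factor. No stratum is defined elsewhere in the protocol.

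**The concern.** Both sections concern the same analysis and the same three tests, and both call their level a Bonferroni level, yet the levels differ. For three comparisons Bonferroni gives 0.05/3 = 0.0167. The 0.025 in section 3.2 is 0.05/2, the level for two.

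If 0.025 went into the calculation and 0.0167 governs the analysis, the 90% belongs to a less strict test than the one planned, and the planned test has less power. The stratum phrase adds a second difficulty. Read literally, it says each comparison is powered inside a subgroup that the design does not have, so a reader cannot match the power statement to any planned analysis.

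**Working it through.** **Inputs.** From section 3.2: p1 = 0.25, p2 = 0.35, difference 0.10, power 90%, four time points, 324 per arm, losses of 10% + 10% + 10% per year. From section 3.1: two years of follow-up. Test levels: 0.025 (section 3.2) and 0.0167 (section 11.3.1), both two-sided.

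**Formula.** Observations per arm for two proportions with pooled variance under the null:

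m = [ z(1−α/2)·√(2·p̄·(1−p̄)) + z(0.90)·√(p1(1−p1) + p2(1−p2)) ]² / (p2−p1)²

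Here p̄ = 0.30, so the first root is √0.42 = 0.6481. The second is √(0.1875 + 0.2275) = √0.415 = 0.6442. z(0.90) = 1.2816.

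**Step 1: reproduce the plan's figure at 0.025.** z = 2.2414.

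- m = (2.2414 × 0.6481 + 1.2816 × 0.6442)² / 0.01 = (1.4526 + 0.8256)² / 0.01 = 519.0 observations per arm.
- Women with four independent answers each: 519.0 / 4 = 129.8.
- Losses added: 3 × 10% × 2 years = 60%, so 40% are retained. 129.8 / 0.40 = 324.4 per arm, against the stated 324.
- Power check: 324 × 4 × 0.40 = 518.4 observations per arm. (0.10 × √518.4 − 1.4526) / 0.6442 = 1.279, and Φ(1.279) = 0.900.

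So 324 and 90% go together at 0.025 with no stratum in the calculation. Other choices do not reproduce the figure:

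| Change from Step 1 | Women per arm |
|---|---|
| Level 0.05 | 275 |
| Level 0.0167 | 354 |
| Continuity correction | 337 |
| Losses compounded (0.7² = 0.49 retained) | 265 |

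**Step 2: the planned level of 0.0167, all else unchanged.** z = 2.393, and 2.393 × 0.6481 = 1.551.

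- Power with 518.4 observations per arm: (2.2768 − 1.5510) / 0.6442 = 1.127, and Φ(1.127) = 0.870.
- For 90% power: m = (1.5510 + 0.8256)² / 0.01 = 564.8, which rounds up to 565. 565 / 4 / 0.40 = 353.1, so 354 per arm and 3 × 354 = 1,062 in total. That is 90 more than 972.

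**Step 3: the stratum phrase.** Section 3.2 refers to strata. Section 6.3.2 names none, and the model in section 11.3.1 has no stratum term and no within-stratum test. Step 1 reaches 324 without dividing the arms, so the phrase did not enter the number. It is an undefined term.

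**The case against.** The strongest reply is that section 11.3.1 already settles how the trial will be judged: three two-sided tests at 0.0167. Section 3.2 only lists planning assumptions, and the gap costs about three points of power. All of that is correct, and it limits the point in three ways.

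- A reader might infer that the decision threshold is unknown, or that the family error is inflated. Neither follows. Three pairwise tests at 0.025 would have a family error of about 6.4% (Bonferroni bound 3 × 0.025 = 7.5%), but the analysis section does not plan those tests. At 0.0167 the family error stays below 0.05.
- A reader might infer that 324 per arm cannot be derived at all, or that power collapses because the arms are split by stratum. Step 1 shows that the number can be derived, and without strata. Any power quoted for a stratum would need the number and size of the strata to be invented.
- It could also be said that the loss model is uncertain. If losses compound (0.49 retained, 324 × 4 × 0.49 = 635 observations), power at 0.0167 is about 93%. That is a fair caution, but that model would have called for 265 per arm, so it is not how the plan reached 972.

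The reply does not remove the mismatch. The protocol prints both levels for the same tests, and the power it claims goes with the one it will not use.

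**Conclusion.** The point holds, at modest size. The 972 women and 90% power in section 3.2 are tied to a level of 0.025. At the 0.0167 set in section 11.3.1 the same calculation gives about 87.0%, and 90% would need about 354 per arm.

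These figures rest on two assumptions inferred from the fact that they reproduce 324: losses are added to 60%, and a woman's four answers are independent. The second matters more than the level itself. With an assumed within-woman correlation ρ of 0.1 to 0.5, the effective observations are 518.4 / (1 + 3ρ), or 399 to 207 per arm, and power at 0.0167 is about 76% to 43%. The protocol gives no value for ρ, so this range only shows why the assumption should be written down.

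The stratum phrase is a separate wording error with no effect on the number.

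**What to change.** Use one level in both sections. There are two consistent ways:

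1. Keep three confirmatory comparisons. In section 3.2 replace 0.025 with 0.0167 and state the power of 324 per arm as about 87%, or raise the target to about 354 per arm if 90% is to be kept.
2. Name only RLP versus control and RLP+ versus control as confirmatory, and use 0.025 in sections 3.2 and 11.3.1. The 972 and 90% then stand on the plan's own assumptions, and RLP versus RLP+ becomes supportive.

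Either way, state in section 3.2 how the losses were combined and that the four time points were treated as independent. Delete the stratum phrase, or define the strata and carry them into sections 6.3.2 and 11.3.1.

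The cost is protocol wording. The first option lowers the stated power by three points or adds about 90 women; the second gives up a confirmatory claim on the two tools against each other. A closed test (a three-group test at 0.05, then each pair at 0.05) could replace Bonferroni and recover power, but this is optional, since Bonferroni at 0.0167 is valid.

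### The 324 per arm fits a calculation in which leavers contribute nothing, but the primary analysis keeps their earlier periods, so the stated 90% is not the power of the planned analysis

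*Protocol*

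**What the plan says.** Protocol section 3.2 plans "972 randomized participants (324 for each of the three study groups"). It says that the Aim 1 binomial regression drives the number, and it presents five assumptions as leading to it:

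- "binomial regression with the proportion of occurrences out of four time points"
- "90% statistical power"
- "two-sided, 0.025 significance level test (Bonferroni correction) comparing RLP to control", and likewise for the other two pairs of arms
- "effect size of 0.10 (difference between rates of 0.25 and 0.35")
- "10% lost to follow-up per year, 10% lost per year for women who change their minds about intending pregnancy, and another 10% lost per year" (the third loss being pregnancy, intended or not)

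The list contains no within-woman correlation. It does not say how the three yearly losses were combined over two years, or what a woman who leaves is taken to contribute.

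Section 11.2.1.1 defines the primary outcome per woman: periods with contraceptive use divided by periods in which she does not intend pregnancy. Section 11.3.1 then says: "The denominator will be four, except for those participants who withdraw consent from the study, change their minds about intending pregnancy during the study", and it adds women who become pregnant to the exception. These women stay in the binomial regression with a denominator below four. Women who stop answering without withdrawing consent are not mentioned in that sentence.

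The significance level also differs. Section 3.2 uses 0.025, whereas 11.3.1 corrects for three comparisons and uses 0.0167.

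**The concern.** Sections 3.2 and 11.3.1 describe the same regression, so the information assumed when sizing the trial should be the information that the regression will use. It appears not to be. A woman who gives two periods and then becomes pregnant counts as two observations in 11.3.1. In the calculation that fits 324 she counts as none.

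The 90% power statement, and so the reason for 972, would then belong to an analysis of completers that the protocol does not plan. The same arithmetic also treats four answers from one woman as four independent observations. Those two simplifications push power in opposite directions, so nobody can tell from 3.2 what power the planned analysis has. A later correction of only one of them would mislead.

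**Working it through.** **Inputs.** From section 3.2: rates 0.25 and 0.35, two-sided 0.025, power 0.90, four periods, three losses of 10% per year, 324 per arm. From section 3.1: two years. From section 11.3.1: periods at 6, 12, 18 and 24 months, reduced denominators, level 0.0167. Not in the protocol, and therefore assumed: the timing of exits and the within-woman correlation (ICC).

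**Step 1: reproduce 324.** Single observations per arm, pooled two-proportion formula:

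n = [z₀.₉₈₇₅ √(2 × 0.30 × 0.70) + z₀.₉₀ √(0.25 × 0.75 + 0.35 × 0.65)]² / 0.10²

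= [2.2414 × 0.6481 + 1.2816 × 0.6442]² / 0.01 = 519.0

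- Four independent periods per woman: 519.0/4 = 129.75 women.
- Losses added: 3 × 10% × 2 years = 60%, leaving 0.40.
- 129.75/0.40 = **324.4**, against 324 stated. The unpooled form gives 321.9 and the arcsine form 323.7.

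Compounding the same losses, with four independent periods, does not fit: 129.75/0.7² = 265 and 129.75/0.9⁶ = 244.

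**Step 2: information and power on that reading.** Periods per arm: 0.40 × 324 × 4 = 518. Power = Φ[(0.10 √N − 2.2414 × 0.6481)/0.6442] with N = 518 gives **90.0%**, as stated.

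**Step 3: apply the 11.3.1 rule, still with independent periods.** Assume exits are even, at 15% of women per six months. The proportions contributing at the four visits are then 0.85, 0.70, 0.55 and 0.40, which sum to 2.50 periods per woman. Periods per arm: 324 × 2.50 = 810, or 56% more than 518. Power is **98.5%**.

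| Exit pattern (assumed) | Mean periods per woman | Periods per arm | Power, level 0.025, ICC 0 |
|---|---|---|---|
| All leavers contribute nothing | 1.60 | 518 | 90.0% |
| Start of each year (0.70, 0.70, 0.40, 0.40) | 2.20 | 713 | 97.1% |
| Even, additive | 2.50 | 810 | 98.5% |
| Compounded, 0.7 kept per year | 2.61 | 846 | 98.8% |
| Compounded, 0.9³ kept per year | 2.74 | 887 | 99.1% |
| End of each year (1, 0.70, 0.70, 0.40) | 2.80 | 907 | 99.2% |

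Section 11.3.1 does not name silent non-responders, so a stricter case drops them entirely (10% × 2 = 20% of women) and lets the other two losses occur evenly. The contributing proportions are 0.70, 0.60, 0.50 and 0.40, a mean of 2.20 periods, or 713 per arm. Power is again 97.1%.

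**Step 4: relax independence.** Under even exits the period counts 0, 1, 2, 3 and 4 have probabilities 0.15, 0.15, 0.15, 0.15 and 0.40. The mean count is 2.5 and the mean squared count is 8.5. The variance inflation is 1 + (8.5/2.5 − 1) × ICC = 1 + 2.4 × ICC, and N = 810/(1 + 2.4 × ICC).

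| ICC (assumed) | Effective N per arm | Power at 0.025 | Power at 0.0167 |
|---|---|---|---|
| 0 | 810 | 98.5% | 97.8% |
| 0.1 | 653 | 95.7% | 94.1% |
| 0.3 | 471 | 86.7% | 83.2% |
| 0.5 | 368 | 76.5% | 71.6% |
| 0.7 | 302 | 67.1% | 61.4% |

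Power equals 90% at an ICC of about 0.23 for level 0.025 (0.15 to 0.32 over the five exit patterns), and about 0.18 for 0.0167 (0.11 to 0.26).

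**The case against.** The strongest objection is that the premise is inferred. Section 3.2 prints neither 60% nor 0.40, and other routes reach about the same number. Partial periods with an unlisted ICC near 0.23 give about 90% power at 324 per arm. A design effect that halves the four periods, with only 20% of women lost, gives 519.0/2/0.80 = 324.4. This stands, so the reconstruction cannot be called the only one. But each of these routes needs an input that is absent from a list presented as what leads to 972. If one of them was used, a decisive assumption is missing and 3.2 needs the same restatement.

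A second objection is that dividing by the retained fraction is a common and cautious planning shortcut, and is not a plan to analyse completers. This also stands: taken alone, the step adds power. A reader might go on to infer that the trial is oversized, because on independent periods 519.0/2.5, or about 208 per arm, would reach 90%. The protocol does not support that inference, because it rests on four answers from one woman being uncorrelated. Nor does the protocol show that the trial is underpowered, since it gives no correlation.

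A third objection is that 11.3.1 is explicit for only part of the losses. That is right, but two of the three loss categories, changed intention and pregnancy, are named, and dropping all non-responders still gives 97.1%.

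A reader might also infer that women with intended pregnancies are counted twice, once as having changed their minds and again as pregnant. The text does not show this. Section 3.2 can be read as listing separate groups, and a woman may change her mind and conceive between two six-monthly surveys.

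**Conclusion.** The power statement is wrong as written. On the inputs that 3.2 lists, 324 corresponds to discarding 60% of women and counting four independent periods from the rest. The regression in 11.3.1 keeps earlier periods for women who withdraw consent, change intention or become pregnant. The stated 90% is therefore not the power of the planned analysis.

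On the protocol's other assumptions the leaver rule alone understates power: about 97–99% instead of 90%, whichever of the five exit patterns is assumed. The independence assumption acts in the opposite direction and can outweigh it, as can be seen from the fall below 90% at an ICC of about 0.23. The stricter level in 11.3.1 lowers power further; on the completers-only arithmetic it alone takes 90% to 87%. The net error has no determinable sign, because the protocol states neither exit timing nor correlation. The conclusion rests on the reconstruction of 324, which is strong but not proven.

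**What to change.** Keep 972, and restate the power in section 3.2 for 324 per arm under the denominator rule of section 11.3.1. The restatement should give:

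- the expected number of evaluable periods per woman, with the assumed timing of exits (about 2.5 of 4 if exits are even);
- how the three yearly losses are combined over two years, and how women who stop responding without withdrawing consent are counted;
- a within-woman correlation, or a range, with power at each value;
- the significance level used in 11.3.1.

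Make these changes together, since correcting one alone would move the figure in a misleading direction. The cost is one recalculation and a rewritten paragraph. Enrolment, data collection and the analysis model do not change.
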